ADL Activities of daily life
ADP Adenosine DiPhosphate
AE Adverse Event
ANCOVA Analysis of Covariance
ASADE Anticipated Serious Adverse Device Effect
BMI Body Mass Index
CMCJ Carpo-Metacarpal joint
CRF Case Report Form
DASH The Disabilities of the Arm, Shoulder and Hand questionnaire
EC Ethics Committee
EL Eaton-Littler
GPIIb-IIIa Glycoprotein IIb and IIIa
HIV Human Immunodeficiency Virus
ICF Informed Consent Form
IEC Independent Ethics Committee
IGF-1 Insulin-like Growth Factor 1
IL-1 Interleukin-1
IL-6 Interleukin-6
IL-8 Interleukin-8
IL-10 Interleukin-10
IL-13 Interleukin-13
IL-17 Interleukin-17
IFN- γ Interferon- γ
IRB Institutional Review Board
JSN/JSW Joint Space Narrowing/Joint Space Width
MMP Matrix Metalloproteinase
MRI Magnetic Resonance Imaging
NSAID Non-Steroidal Anti-Inflammatory Drug
NRS Numeric Rating Scale
OA Osteoarthritis
OOT Oxygen-ozone therapy
PA Posterior-Anterior
pH potential Hydrogen
QL Quality of life
RCT Randomized Controlled Trial
SAE Serious Adverse Event
SADE Serious Adverse Device Effect
SAP Statistical Analysis Plan
TGF- β 1 Transforming Growth Factor beta 1
TMJ trapezio-metacarpal joint
TMJO trapezio-metacarpal joint osteoarthritis
TNF α Tumor Necrosis Factor alpha
UADE Unanticipated Adverse Device Effect
USADE Unanticipated Serious Adverse Device Effect
VAS Visual Analog Scale

1- Introduction

Osteoarthritis is a degenerative condition that causes pain, impaired function and affects daily activities (1). OA of trapezio-metacarpal joint (TMJ) most commonly occurs in women over 50 years old, often bilateral and it is a disabling condition presenting with pain at base of the thumb, swelling, instability, deformity and impairment of hand function with limitation in gripping and pinching objects (2). Several factors have been associated with the development of degenerative changes in the carpometacarpal joint (CMCJ), including increased thumb base joint laxity and greater grip strength. In osteoarthritis, there is the destruction of cartilage and subchondral bone, with the consequent narrowing of articular space. Besides the biomechanical factors, trauma and adiposities, it is believed that inflammation plays an important role (3).

The inflammatory process is supported by several pro-inflammatory cytokines released by chondrocytes. Among these, the most important cytokines are IL1, IL6, IL8, IL17, LIF, TNF- α and IFN- γ , which cooperate in destroying the articular cartilage (4). Furthermore, IL1, which affects the production of ROS (reactive oxygen species), is implicated in the damage to chondrocytes DNA. ROS accelerate the disintegration of the cartilage matrix, and narrowing of the joint space, inhibiting the synthesis of collagen and proteoglycans (3). Another mechanism of joint destruction is proteolytic degradation (4). Based on this, future therapy in OA should inhibit proteolytic enzymes such as metalloproteinases (MMPs), nitric oxide synthesis (NOs), proinflammatory cytokines (IL1, IL6, TNF- α) and apoptosis. On the other hand, OA treatment should stimulate the synthesis of anti-inflammatory cytokines (IL4, IL10, IL13) and growth factors (TGF- β , IGF-1(5). The severity of trapezio-metacarpal osteoarthritis (TMJO) is classified radiologically by Eaton and Litter (6). There are several surgical treatment options for TMJO as well as many conservative treatments such as splinting, thumb strengthening exercises, anti-inflammatory drugs and intra-articular injections. There are no currently approved TMJO treatments capable of slowing OA-related structural progression, (7) so the main goals of the conservative treatment are to provide symptomatic relief, improve joint function, and delay surgical intervention. The patient with symptomatic TMJO in its initial stages are usually treated conservatively before surgical intervention: one of the main actions of intra-articular treatments, ranging from corticosteroids to hyaluronic acid and biologic products is to reduce inflammatory distress within the joint; injection treatments are usually used alone or in combination with thumb splint in a multimodal rehabilitation approach (8\9\10). In recent years, there has been a growing

interest in the effects of ozone (11), which can be safely delivered intra-articularly and whose use is in constant increase in an outpatient setting due to the ease of preparation methods.

1.1. Mechanism of Oxygen-Ozone therapy

Ozone (O₃), a gas discovered in the mid-19th century, is a molecule consisting of 3 atoms of oxygen in a dynamically unstable structure due to the presence of mesomeric states (12). Intra-articular administration of an adequate mixture of oxygen-ozone is supposed to reduce pain, to have protective immunomodulatory effects on cartilage, and to reduce oxidative stress, thus potentially representing an alternative to other injective methods (13). Several researchers worldwide and many years of clinical experience have indicated that O₃ has the capacity to modulate inflammation (3). O₃ is highly reactive and, when injected into a joint capsule, it is able to stimulate fibroblastic joint repair, reduce inflammation, and may promote new cartilage growth (3). O₃ produces acute oxidative stress with a paradoxical antioxidant effect: it has been shown that the controlled administration of O₃ may promote an oxidative preconditioning or adaptation to oxidative stress that in turn stimulates the antioxidant endogenous system, finally resulting in a protective state against tissue damage (14). When injected into the trapeziometacarpal joint, O₃ is mixed with oxygen (O₂) and dissolves into the synovial fluid, which contains antioxidants and proteins, and generates reactive oxygen species and lipid oxidation products. These molecules inactivate and inhibit proteolytic enzymes, decrease the release of proinflammatory cytokines, induce the proliferation of chondrocytes and fibroblasts, and promote the synthesis of antioxidant enzymes and immunosuppressive cytokines (15). All these processes counteract the proinflammatory and pro-oxidative circuit that arises in TMJO, resulting also in an increase in tissue oxygen supply through a hemorheologic action based on vasodilatation and angiogenesis stimulation (12).

1.2. Clinical Experience

From the literature, it is widely accepted that ozone has the biological properties of inducing analgesia, anti-inflammatory, and antioxidant effects mediated by activating the cellular metabolism and inhibiting prostaglandin synthesis (16), reduce edema and inflammation (17\18\19\20), and therefore reduce pain and improves function in OA (11\17\21\22\23\24\25\26). Intra-articular oxygen-ozone has been used in the medical domain for several decades. Although some articles have reported promising results on the effectiveness of oxygen-ozone for example in knee or temporomandibular OA, the evidence is low (17).

Many authors claim ozone is a good treatment with high success rate, minor complications and easy execution, reproducibility and sustainable outcome (17); however is still unclear what best therapeutic protocol is in terms of ozone concentration, volume to be injected, number of injections and time between injections. Patients could recovery the hand functions, pinch and grip movements.

1.3. OOT machine Description

Certified equipment "Medical Device Directive 93/42/CEE and S.M.I. in IIA class" and compliant with S.I.O.O.T. protocols. MEDICAL 99 IR is a portable unit for oxygen-ozone therapy, made for exclusively medical and/or research use.

MEDICAL 99 IR ensures consistent and repeatable conditions of use and ensures maximum reliability. The oxygen-ozone mix generator is operated by a microprocessor, which controls and displays the ozone concentrations produced, available according to ten custom selections. The equipment allows the withdrawal of the gas mixture in a state of total safety, carefully monitoring the chosen concentration. MEDICAL 99 IR guarantees the absolute purity of the gas delivered.

1.3.1. Indications for Use

The oxygen-ozone is injected inside the TMJ for the treatment of osteoarthritis and associated symptoms.

1.3.2. Contraindications

Contraindications: favism, pregnancy, severe cardiovascular diseases, hematological and respiratory failure, cancer and thyreopathies.

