1.4.2. Contraindications

Contraindications: discomfort regarding the use of the splint, venous or lymphatic stasis present in the relevant hand.

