2.2. Eligibility Criteria

Inclusion criteria

- 1- Male or female at least 18 years of age at time of screening.
- 2- Ability to comply with study procedures and visit schedules and able to follow oral and written instructions.
- 3- Patients with symptomatic OA in one thumb joint from 3 months. If bilateral, the side with major symptoms will be considered.
- 4- A thumb joint radiograph showing a E-L grade of 1 to 3 and an absence of severe osteoarthritis (defined as advanced stage osteoarthritis, including large osteophytes, chronic fractures or bone remodeling, severe deformity or bone attrition, and/or bone-on-bone contact indicative of severe osteoarthritis/full thickness cartilage loss).
- 5- Has undergone at least one prior conservative OA treatment (e.g. physical therapy, simple analgesics).
- 6- Signed an ethics committee-reviewed approved informed consent form.

Exclusion criteria

- 1- Presence of clinically observed active infection or severe inflammation in the index trapeziometacarpal joint or skin disease/breakdown or infection in the area of the planned injection site of the index thumb joint.
- 2- Diagnosed with rheumatoid arthritis, Reiter's syndrome, psoriatic arthritis, gout, ankylosing spondylitis, or arthritis secondary to other inflammatory diseases; Human Immunodeficiency Virus (HIV), viral hepatitis; chondrocalcinosis, Paget's disease, or villonodular synovitis.
- 3- Diagnosed with leukemia, known presence of metastatic malignant cells, or ongoing or planned chemotherapeutic treatment.
- 4- Disease of cervical spine, shoulder or other upper extremity joints judged by the investigator to be contributing to the pain in the index thumb joint (e.g. radiculopathy, De Quervain S., ecc).
- 5- Untreated symptomatic injury of the index hand (e.g., acute traumatic injury, tendinopathy, nerve lesion).
- 6- Presence of surgical hardware or other foreign body intended to treat arthritis or cartilage-related pathology in the index thumb joint.
- 7- Presence of venous or lymphatic stasis in the index arm.
- 8- Orally administered systemic steroid use within 2 weeks prior to screening
- 9- Planned/anticipated surgery of the index hand during the study period.
- 10- Major surgery of the index hand within 12 months prior to screening.
- 11- Minor surgery (e.g. arthroscopy) of the index hand within 6 months prior to screening.

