- 12- Any documented clinically significant degree of cognitive impairment or other condition, finding, or psychiatric illness at screening, which, in the opinion of the investigator, could compromise patient safety or interfere with the assessment of the safety and treatment effects of the study injection.
- 13- Pregnant or nursing mothers or women planning to become pregnant during the time they will be participating in the study.
- 14- Previously documented failed treatment with OOT or splint
- 15- Known drug or alcohol dependence currently or within the last year.
- 16- Use of any investigational drug or device within 30 days prior to screening.
- 17- Use of any investigational biologics within 60 days prior to screening.

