2.4.1.4. Baseline Recording

During the screening visit, the following information will be obtained and recorded in the subject study record and CRFs for all subjects.

- Signed and dated original ICF

- Inclusion and exclusion criteria
- Demographics
- Relevant Medical history, baseline conditions and medication use

The following baseline assessments will be completed prior to treatment and after final eligibility confirmation (during injection visit and prior to the injection procedure itself).

- VAS
- Grip strength test
- Tip pinch strength test
- Kapandji Score
- Nine-Hole Peg Test

All preoperative procedures are to be completed within 28 days prior to the injection procedure.

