2.4.4. Injection Procedure

Administer the contents of the syringe as a single injection into the joint. The procedure for the injection involves the following steps:

1. Clean the injection area with an antiseptic solution.
2. Apply a local anesthetic on the injection site (optional). If local anesthetic is used, then a topical anesthetic, such as ethyl chloride, is recommended. Under no circumstances may the anesthetic be injected intra-articularly.
3. Position needle into the intra-articular space and confirm needle placement with an ultrasound image (if ultrasound guidance is being used).

4. Attach an empty syringe to the needle, aspirate all available joint fluid (aspiration volume must be recorded).
5. Transfer the syringe that contains the injection solution to the needle positioned at the injection site.
6. Inject all contents of the syringe into the synovial space of the joint. (Take care not to inject extra-articularly or into the synovial tissues and capsule).

A clear ultrasound image is to be taken to document needle placement in the synovial space. Any AEs associated with joint aspiration and injection procedure will be recorded. Additionally, any device processing issues will be recorded. Before discharge subjects will be instructed not to exceed their pre-injection physical activity level for 14 days post-injection.

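### Five of the seven ozone contraindications in section 1.3.2 are not named as exclusions and cancer is only partly excluded, so keeping these patients from ozone injections rests on investigator judgement

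*Combined protocol and SAP*

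**What the plan says.** Section 1.3.2 gives the contraindications to the ozone treatment: "Contraindications: favism, pregnancy, severe cardiovascular diseases, hematological and respiratory failure, cancer and thyreopathies". Section 1.4.2 does the same for the splint: "Contraindications: discomfort regarding the use of the splint, venous or lymphatic stasis present in the relevant hand".

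The exclusions in section 2.2 that bear on these lists are:

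- Exclusion 3: "Diagnosed with leukemia, known presence of metastatic malignant cells, or ongoing or planned chemotherapeutic treatment".
- Exclusion 7: "Presence of venous or lymphatic stasis in the index arm".
- Exclusion 12, which in addition to cognitive impairment covers any "other condition, finding, or psychiatric illness at screening, which, in the opinion of the investigator, could compromise patient safety".
- Exclusion 13: "Pregnant or nursing mothers or women planning to become pregnant during the time they will be participating in the study".

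Section 2.6.2 itemises the medical history: systemic inflammatory conditions, active malignancy, pregnancy, lactation, leukemia and current chemotherapy. Section 2.4.1.4 adds a general screening entry, "Relevant Medical history, baseline conditions and medication use". The assessments listed under section 2.4.1.3 for confirming eligibility are the DASH and an X-ray.

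Section 2.5.2 lets the investigator withdraw a subject who, on the day of injection, is no longer suitable for it, and such a subject is replaced. The same section also lets the investigator withdraw any patient at any time on medical judgement. Sections 2.5.1 and 4.4.1 take subjects who were given no study treatment out of the intent-to-treat population and out of the sample-size count.

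**The concern.** A contraindication declared in the protocol should normally appear as a fixed eligibility check. This protocol does that elsewhere: the stasis contraindication for the splint became exclusion 7, and pregnancy became exclusion 13. Most of the ozone list did not follow. The gap is therefore an inconsistency between the protocol's own sections and does not depend on an outside clinical preference.

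The main stake is patient safety. Subjects in the ozone arm are to receive two intra-articular injections (section 1.7 and Appendix A). Whether someone with, say, favism is kept out depends on the investigator asking about it and acting on the answer.

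The secondary stake is comparability. Only one arm is injected, so a condition that matters only for ozone, and is noticed between randomisation and the first injection, is a reason to withdraw an ozone patient but not a splint-only patient.

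**Working it through.** The check is a comparison of lists. Each item in section 1.3.2 was looked up in the exclusions of section 2.2 and in the history items of section 2.6.2. General wording was not counted as naming a condition, and leukemia was not counted as cover for hematological failure.

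| Item in 1.3.2 | Named in 2.2? | Itemised in 2.6.2? |
|---|---|---|
| Favism | No | No |
| Pregnancy | Yes (exclusion 13) | Yes |
| Severe cardiovascular disease | No | No |
| Hematological failure | No | No |
| Respiratory failure | No | No |
| Cancer | In part (exclusion 3) | Yes (active malignancy) |
| Thyroid disease | No | No |

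**Count against 2.2.** 1 in full + 1 in part + 5 not named = 7. With the two kinds of failure read as one item, 1 + 1 + 4 = 6.

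**Count against 2.6.2.** 2 itemised + 5 absent = 7, or 2 + 4 = 6. The absent items are the same ones.

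**Cancer.** Exclusion 3 applies to leukemia, known metastatic disease, and current or planned chemotherapy. A patient with an active, non-metastatic solid tumour and no chemotherapy is captured as a history item in 2.6.2 but meets none of these conditions. For this item the history and the exclusions disagree.

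**Late detection.** The steps are:

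1. The injection-day rule in 2.5.2 turns on fitness for injection.
2. Under section 2.4.2 only the ozone-plus-splint arm is injected.
3. An ozone patient found to be contraindicated after randomisation but before the first injection can be withdrawn under that rule, and is then replaced.
4. The same finding in a splint-only patient triggers nothing under that rule, because there is no injection to withhold.

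This establishes a possible one-sided route. To size it would need the frequency of these conditions, the share found late and their relation to the DASH outcome. The documents give none of the three.

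**Sample size.** Section 7.1 plans 16 per group for a 1 SD difference, raised to 20 per group for losses. The normal-approximation formula gives 2 × (1.960 + 0.842)² / 1² = 15.7, so 16, which reproduces the plan's figure. Exclusions applied before randomisation do not enter this calculation, so 16 and 20 per group stand.

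**The case against.** The strongest reply is that the protocol already has a suitable criterion. Exclusion 12 is one of the 17 numbered exclusions, applies at screening and covers both arms. A condition that the same protocol calls a contraindication fits its wording well. General history is recorded for all subjects at screening, only eligible subjects are randomised, and most of these conditions are long-standing and may well be found then. This stands in part. A reader might infer that patients with the unnamed conditions satisfy every criterion and will be enrolled. The documents do not support that, because an investigator applying exclusion 12 can keep them out. What remains is that exclusion 12 names none of them and works only if an opinion is formed.

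A reader might also infer from 2.6.2 that these conditions will go unrecorded. That does not follow either. Section 2.6 is not exhaustive: under section 2.4.4 the "aspiration volume must be recorded", and section 7.3 tests race, yet neither is listed in 2.6. The case report forms and the Appendix B figure cannot be seen.

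On comparability the reply is stronger:

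- The power in 2.5.2 to withdraw on medical judgement applies to either arm, so removal from the ozone arm alone is an inference about practice and not a stated rule.
- The injection-day clause is written for a subject who has become unsuitable, with new joint infection as its example. The documents do not show that the 1.3.2 conditions would surface that late.
- Removal from the intent-to-treat population is not certain. Sections 2.5.1 and 4.4.1 require that no study treatment was given. The ozone arm also receives splints, and the documents do not say whether these are fitted before the first injection.
- The one-sided effect comes from the withdrawal and replacement rules, which any reason for withholding the injection could trigger. Aligning the lists removes only one such reason.

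**Conclusion.** The mismatch is certain: 5 of 7 declared ozone contraindications (4 of 6 on the joined reading) are neither named in 2.2 nor itemised in 2.6.2, and a sixth, cancer, is only partly excluded. The count assumes only that general wording does not name a condition and that leukemia is not hematological failure. The consequence that holds is about safety and consistency: a patient with a declared contraindication could be randomised to ozone unless the investigator's judgement intervenes. This should be fixed.

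The comparability point is secondary and holds only as a possibility. A reader might infer that late detection will remove patients from the ozone arm only and bias the DASH comparison. The text does not establish that such detections will occur, that investigators will treat the arms differently, or that the patients removed differ in outcome. Any percentage of ozone patients lost this way would restate an assumed count. Neither the size nor the direction of bias can be shown.

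**What to change.** Amend section 2.2 to exclude favism, severe cardiovascular disease, hematological failure, respiratory failure, thyroid disease in clinically qualified terms (for example, uncontrolled disease) and any active cancer. Add matching history items to section 2.6.2 and the screening form. Check them in every candidate before randomisation, so that the check is the same whichever arm follows.

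The sponsor's clinicians should settle two matters first. The thyroid item, copied unqualified, would exclude any thyroid disease however mild or well controlled. Any item they judge not to apply to intra-articular use should be deleted from 1.3.2. Either way, 1.3.2, 2.2 and 2.6.2 should end up in agreement.

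The cost is amendment wording, a few form items and some additional screen failures, whose number cannot be estimated from the documents. The sample size and the analysis do not change.

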1.4. Thumb Splint

It is a functional thermoplastic splint for the stabilizing of the TMJ, maintaining the pulp of the distal phalange of the index finger free for gripping with the other fingers and leaving the thumb in a functional position.

1.4.1. Indications and Usage

Splints for TMJO provide external support to the joint, thereby stabilizing the adjacent joints capable of compensatory movements and maintaining the first joint space.

1.4.2. Contraindications

Contraindications: discomfort regarding the use of the splint, venous or lymphatic stasis present in the relevant hand.

1.5. Use and Training

Appropriate investigative site personnel will be trained on OOT syringe processing and preparation of the splint. The investigator or other personnel who will be administering treatment should have the appropriate medical training to give intra-articular trapezio-metacarpal injections.

1.6. Current Study Rationale

The aim of this study is to compare the effectiveness of combined treatment with intra-articular ozone injections and joint splinting in comparison to only thumb splint therapy in patients with TMJO by evaluating the following aspects:

- Clinical improvement of TMJO
- Reduction of pain
- Improvement in functional aspects of the thumb
- Improvement in patient's quality of life

